## PRÉCIS

Prevention of oral chronic graft versus host disease (GVHD) by topical agents is an attractive strategy because it would potentially avoid the adverse effects associated with systemic immunosuppression. Topically administered dexamethasone solution is a commonly used agent for the prophylaxis of oral inflammatory conditions including GVHD. However, the efficacy and systemic effects of topically administered dexamethasone solution are unknown. We therefore propose this trial designed to evaluate the efficacy and safety of topical dexamethasone solution for prevention of oral chronic GVHD in stem cell transplant recipients.

This pilot phase II study will follow a randomized, double-blind, placebo controlled, parallel group design. Consenting subjects who have undergone hematopoietic stem cell transplantation at the NIH Clinical Center and the surrounding transplant clinics will be randomized 50/50 to receive dexamethasone 0.01% solution or placebo as an oral rinse for 3 months starting 90-100 days post-transplant. Subjects will be evaluated monthly after the start of intervention. Diagnostic and research evaluations will include a complete oral examination, oral mucosal biopsy prior to the beginning of the intervention (day -7) and at the time of development of oral chronic GVHD or at the completion of intervention in the absence of clinical GVHD. We will measure serum dexamethasone levels and perform short cosyntropin (ACTH stimulation) test at the end of the 3 months of intervention or onset of clinically significant GVHD.

The primary objective of the study is to evaluate the safety and efficacy of topical dexamethasone 0.01% solution used as an oral rinse for prevention of oral chronic GVHD. Our primary endpoint will be the proportion of subjects that develop clinically significant (severity score 3 or higher) oral chronic GVHD after three months.

Secondary objectives will include the impact of oral chronic GVHD on the quality of life, characterization of the changes in tissue and salivary biomarkers associated with development of oral graft versus host disease, and measures of the effects of topical dexamethasone on hypothalamo-pituitary-adrenal axis. Secondary outcomes will include oral cavity specific quality of life as measured by OHIP-14 questionnaire, oral discomfort levels, improvement in general quality of life scores, and severity of oral chronic GVHD as measured by the site-specific GVHD scoring system.

---

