## 1.2 Secondary Objectives

- 1.2.1 To assess the incidence, risk factors and clinical characteristics of oral chronic GVHD.
- 1.2.2 To evaluate the impact of oral chronic GVHD on quality of life.
- 1.2.3 To evaluate the degree of systemic absorption of topical dexamethasone and its effect on adrenal cortical function.
- 1.2.4 To evaluate changes in salivary and plasma proteome associated with oral chronic GVHD.
- 1.2.5 To evaluate tissue kinetics and gene expression patterns of immune cells associated with the development of chronic oral GVHD and prophylaxis with topical dexamethasone.
- 1.2.6 To assess the predictive value of subclinical tissue changes on development of chronic oral and systemic GVHD and prognostic significance of these changes in terms of graft versus tumor effect.

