### **5.2.2 *Post transplant medications***

There will be no prohibited interventions for this study except topical agents for oral GVHD. All interventions and medications dictated by the subject's primary transplant protocol and clinical necessity will be permitted. Subjects will be queried at interim assessments regarding topical and systemic analgesic use. Factors that can potentially confound the results (such as systemic steroids and other immunosuppressants) will be tracked and taken into consideration at the time of the final statistical analysis.

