#### **6.1.2 Baseline assessments**

- Serum chemistry (Acute Care (Na, K, Cl, CO2, Creatinine, Glucose, and Urea Nitrogen), Mineral (Phosphorus, Magnesium, Albumin, and Calcium), Hepatic (Alk Phosphatase, ALT, AST, Total Bilirubin, and Direct Bilirubin), and Other (Total Protein, CK, Uric Acid, and LD) panel) done concurrently with post transplant monitoring
- Pregnancy test (females of child bearing potential)
- Serum cortisol level (results blinded to investigators)
- The 0-10 Scale for Oral Pain (see Appendix A)
- The 0-10 Scale for Oral Xerostomia (see Appendix A)
- GVHD Severity Scale (see Appendix B)
- Lichen Planus (Oral GVHD) Severity Scale (see Appendix C)
- Disease specific quality of life - OHIP-14 scale (ages 18 and older only-Appendix D)
- Oral photographs (Optional)
- Oral lesion documentation
- Buccal mucosal less than approximately 6mm punch biopsy (ages 18 and older only) (optional)
- Research blood sample collection
- Research saliva sample collection
- Growth chart (length for age, weight for age percentiles and body mass index for age percentiles, pre-pubertal children) (if a hand x-ray is available on parent transplant protocol, the results will be reviewed)

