#### 8.4.6 Assessment of adrenocortical function (cortisol levels)

Subjects will be evaluated for possible hypothalamic-pituitary axis (HPA) axis suppression with the following measures:

1. Morning cortisol levels will be determined at baseline, monthly follow-ups (done at NIH), and at completion of the interventional phase (3 months after the last dose of study medication). The results will be blinded to the investigators until the end of the study. At the end of the study, in subjects with morning cortisol levels between 19 mcg/dL and 3 mcg/dL no further adrenal function testing will be performed.
2. In subjects with the symptoms of suspected adrenal insufficiency, a Short Cosynthropicin Test (SCT) will be performed to determine if the subject has HPA axis suppression. In brief: venous blood will be collected before administration of 250 mcg of cosyntropicin (synthetic ACTH) around 8 AM to 12 noon, and at 30 and 60 minutes after. The expected rise in cortisol levels is to at least 18 mcg/dL (24). In cases of minimally abnormal SCT (stimulated cortisol values of 13-17 mcg/dL), the test will be repeated the next day, as it has been demonstrated that the result is often normal with a repeat test. This test has been shown to be sensitive and specific for evaluation of subclinical adrenal suppression [52, 53]. In the unlikely event of significant adrenal suppression as assessed by repeat ACTH stimulation test, Clinical Center Endocrinology Service will be consulted. Pharmacy will be requested to unblind therapy to the endocrinologist so that appropriate therapy can be initiated and the endocrinologist can appropriately attribute the relationship of the event to study drug administration.
3. The confounding effect of systemic corticosteroids will be taken into account at the time of analysis. We expect to have a subgroup of subjects who will not receive systemic steroids. This subgroup will be used to evaluate the effects of topical dexamethasone on adrenal secretion.

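### The rinse's adrenal effect is to be judged in a steroid-free subgroup with no time window, formed at least partly after randomisation, and no cortisol analysis is specified

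*Combined protocol and SAP*

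**What the plan says.** Objective 1.2.3 is "To evaluate the degree of systemic absorption of topical dexamethasone and its effect on adrenal cortical function".

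Section 8.4.6 item 3 addresses systemic steroids in three steps. It opens with a general promise, naming no method, to allow for their confounding in the analysis. It next states an expectation about who will be available: "We expect to have a subgroup of subjects who will not receive systemic steroids". It then gives that group its purpose, which is the point at issue here: "This subgroup will be used to evaluate the effects of topical dexamethasone on adrenal secretion". It gives no time window, expected size or comparison for this subgroup.

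Section 5.2.2 allows all medication that is clinically needed, apart from topical agents for oral GVHD, and adds: "Factors that can potentially confound the results (such as systemic steroids and other immunosuppressants) will be tracked".

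Morning cortisol is listed in 8.4.6 item 1 as an adrenal measure. It is scheduled at baseline in 6.1.2 ("Serum cortisol level (results blinded to investigators") and again at the 3-month visit in 6.3; neither entry is marked optional.

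Section 8.5 states an intention-to-treat principle covering all randomised subjects. It names a chi-squared test for the primary endpoint and a Wilcoxon test for severity, pain, xerostomia and OHIP-14 scores. It promises adjustment for covariates and stratified analyses for systemic immunosuppression, without a model. Cortisol, the ACTH result and the dexamethasone level do not appear there.

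On the ACTH test, 8.4.6 item 2 says "In subjects with the symptoms of suspected adrenal insufficiency, a Short Cosynthropicin Test (SCT) will be performed", whereas the Précis says the study will "perform short cosyntropin (ACTH stimulation) test at the end of the 3 months of intervention"; its alternative time point is when clinically significant GVHD appears.

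**The concern.** Whether a subject stays free of systemic steroids is, at least in part, decided after allocation. Section 2.4.1 describes systemic corticosteroids as the usual treatment for GVHD, and the rinse is meant to reduce oral GVHD. If the rinse changes who receives steroids, the steroid-free subjects in the two arms are selected differently and randomisation no longer protects the comparison. An apparent adrenal effect could then be selection, or a real one could be blurred.

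The baseline cortisol would recover some precision and absorb part of any imbalance in earlier steroid exposure, but no analysis is written that uses it. The ACTH test does not clearly fill the gap, because the documents disagree on who has it. A test done only for symptoms, or only in those who opt in, does not estimate the rate of suppression by arm.

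**Working it through.** **The plan's own figure.** Section 8.2 gives 36 per arm for 15% versus 45%, 80% power and 0.05. With p̄ = 0.30, n = [1.960·√(2·0.30·0.70) + 0.842·√(0.15·0.85 + 0.45·0.55)]² / 0.30² = (1.270 + 0.515)² / 0.09 ≈ 35.4, so 36 per arm; power at 36 is 80.7%. It reproduces (two-sided, no continuity correction), but it concerns the primary endpoint. No figure is given for cortisol or the ACTH test, so what follows rests on assumptions.

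**Size of a selection effect.** Assume no true adrenal effect and a standard-normal severity U. Subjects above a cut-point c on U receive systemic steroids, and U correlates −ρ with cortisol. Among the steroid-free, mean cortisol is ρ·φ(c)/Φ(c) in SD units.
- Steroid use 45%: φ/Φ = 0.396/0.55 = 0.720.
- Steroid use 30%: 0.348/0.70 = 0.497.
- Steroid use 15%: 0.233/0.85 = 0.274.

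Rinse minus placebo, with placebo use at 45%:
- Rinse use 30%: (0.497 − 0.720)ρ = −0.07 SD (ρ = 0.3) to −0.11 SD (ρ = 0.5).
- Rinse use 15%: (0.274 − 0.720)ρ = −0.13 SD (ρ = 0.3) to −0.22 SD (ρ = 0.5).
- Equal use in both arms: 0.

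The documents give neither the steroid-use rates nor ρ. The widest contrast sets steroid use as far apart as the planned endpoint rates, which is an extreme choice.

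**Gain from baseline cortisol.** With correlation r between baseline and end-of-intervention cortisol, the standard error is multiplied by √(1 − r²). For r = 0.3 this is √0.91 = 0.954, a cut of about 5% (variance 9%). For r = 0.6 it is √0.64 = 0.80, a cut of 20% (variance 36%). The range for r is assumed.

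**What each set can detect.** At 80% power the detectable difference is (1.960 + 0.842)·√(2/n) SD.
- All 36 per arm: 0.66 SD unadjusted; 0.66 × 0.954 = 0.63 SD at r = 0.3 and 0.66 × 0.80 = 0.53 SD at r = 0.6.
- Steroid-free share of 75%, 50% or 25% (assumed; 27, 18 or 9 per arm): 0.76, 0.93 or 1.32 SD unadjusted.

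The all-randomised figures suppose that systemic steroids change neither the spread nor the effect, so they are a best case.

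**Statements on the ACTH test, side by side.**
- Précis: at 3 months, or at onset of clinically significant GVHD.
- 6.3: optional at the 3-month visit.
- 8.4.6 item 2: on symptoms, yet supported there as a test for subclinical suppression. Item 1 also makes further adrenal testing depend on the cortisol value.
- 5.4.2: presupposes abnormal results in subjects without symptoms.
- 10.3.1: calls the symptoms non-specific and very common in hospital patients.

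**Statements on cortisol timing, side by side.**
- 8.4.6 item 1 places the completion sample 3 months after the last dose; 6.3 places it 3 months after starting.
- 8.4.6 item 1 lists cortisol at monthly follow-ups done at NIH; 6.2 lists none at months 1 and 2.
- Subjects who reach the endpoint early have the end-of-study assessments and leave the study (5.3, 8.5, 8.8.2). The list in 6.5 has no cortisol, although the Précis foresees dexamethasone and ACTH testing at GVHD onset.

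**The case against.** The best case for the plan is that restricting to subjects without systemic steroids is a reasonable way to isolate topical absorption, because systemic steroids suppress cortisol themselves. That stands. A main set defined by steroid use at baseline would keep later starters; if there were more of them on placebo, placebo cortisol would fall and a rinse effect could be masked. Neither set is free of bias, so the second should accompany the first rather than disappear.

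Four stronger readings are tempting, and the documents do not support them.
- A reader might infer that baseline cortisol will be ignored. No text says so: 8.4.6 lists it as a measure and 8.5 promises adjustment for covariates of interest. What can be said is that no cortisol analysis is specified.
- A reader might infer that ACTH testing is symptom-triggered only. That is one of several conflicting statements, and serial morning cortisol is also a stated adrenal measure.
- A reader might apply the 15% and 45% endpoint rates to count how many subjects each arm loses to steroids. This does not follow. Endpoint subjects have their end-of-study assessments and go off study, with GVHD treatment then left to the transplant team (5.3), so a sample at that point would generally precede treatment. Steroids for GVHD outside the mouth remain possible, but the rinse may not alter that use and the documents do not quantify it.
- A reader might take post-randomisation membership as stated. It is a fair inference from the future tense in 8.4.6 and from 5.2.2, not explicit text.

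It is also fair that the illustrated bias of 0.07 to 0.22 SD is small beside the 0.76 to 1.32 SD the subgroup could detect.

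**Conclusion.** The point holds in a limited form. The only analysis set named for the adrenal effect is undefined in time, is formed at least partly after randomisation and may differ by arm. No cortisol analysis is specified, although cortisol is scheduled at baseline and at 3 months. The passages on who has the ACTH test, when the final cortisol is taken, and what happens to subjects who reach the endpoint early contradict one another.

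The possible bias is modest under the inputs tried (0.07 to 0.22 SD, zero with equal steroid use), and the gain in standard error from baseline adjustment is about 5 to 20%. Both rest on assumed rates and correlations and are illustrative. This is a secondary objective and the primary result is unaffected, but the analysis should be settled before unblinding because the correction is cheap.

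**What to change.** In 8.4.6 and 8.5:
- Compare end-of-intervention morning cortisol between arms by ANCOVA (log or rank scale if skewed), with baseline cortisol and conditioning stratum as covariates.
- Report it in two sets: all randomised subjects with a cortisol value (or those steroid-free at baseline), and those free of systemic steroids up to the cortisol sample. State that the second is not a randomised comparison and that the first includes steroid starters.
- Tabulate by arm how many start systemic steroids and how many have no cortisol value.
- Treat ACTH tests done for symptoms or by choice as descriptive safety data, not as an estimate of suppression by arm.

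Reconcile the Précis, 5.4.2, 6.3 and 8.4.6 on who has the ACTH test and when. Reconcile 8.4.6 with 6.2 and 6.3 on cortisol timing, and 6.5 with the Précis on testing in subjects who reach the endpoint early. Which version is right is for the sponsor to decide.

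The cost is analysis-plan wording, a little extra analysis and a protocol clarification. The data are mostly scheduled already, but whether early-endpoint subjects have a usable cortisol value depends on how those passages are reconciled.

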### 8.5 Data Analyses

This study will be analyzed according to the “intent to treat” principle, that is, all randomized subjects will be included. Subjects not evaluated for endpoints will be considered to have reached the primary endpoint. Every effort will be made to reach and evaluate the subjects at the monthly intervals and at the end of the 3 month intervention period. The differences in proportions of significant oral chronic GVHD will be assessed by a chi-squared test (with continuity correction). Treatment group differences in the severity scores, pain and xerostomia scores, and quality of life scores (OHIP-14) will be assessed using the Wilcoxon test. Adjustments will be made for age and other covariates of interest, such as systemic immunosuppression. Adverse events will be tabulated by severity and treatment assignment. For pediatric subjects, analyses will include growth assessment (growth chart [length for age, weight for age percentiles

and body mass index] for age percentiles) and bone age and the associated z-scores (the number of standard deviations the child's measures [weight, height etc] differ from the population mean).

The intervention period will be 3 months. Should the subject reach the primary endpoint (development of clinically significant oral chronic GVHD), the subject will be asked to participate in end of study assessments and then will go off study. Subjects who did not develop oral chronic GVHD in the intervention phase of the study will be followed for up to 6 months to document late development of oral chronic GVHD. All subjects will be evaluated after 6 months after completion of the intervention phase of the study in the absence of clinical oral GVHD. Final statistical analysis will be performed once all subjects in the sample have completed the study and all records have been collected. We will use stratified analyses to account for effects of systemic immunosuppressive agents and other prognostic factors.

In the event of a protocol violation, the aggregate data will be analyzed with and without those subjects involved in the incident.

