### **8.4 Secondary Endpoints**

#### **8.4.1 Scale for Oral Pain, xerostomia**

Oral discomfort and xerostomia will be measured by 0-10 scale (Appendix A). We will use this scale to evaluate changes in oral pain and xerostomia over the course of treatment at end of study.

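### Section 8.5 names no method for the promised adjustment of the secondary scores and omits the baseline score and conditioning stratum as covariates, which can forgo precision for pain, xerostomia and OHIP-14

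*Combined protocol and SAP*

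**What the plan says.** Section 8.5 gives one test for all the secondary scores: "Treatment group differences in the severity scores, pain and xerostomia scores, and quality of life scores (OHIP-14) will be assessed using the Wilcoxon test". The next sentence adds: "Adjustments will be made for age and other covariates of interest, such as systemic immunosuppression". Later the same section says: "We will use stratified analyses to account for effects of systemic immunosuppressive agents and other prognostic factors". It names no regression model, stratified rank test or rank-based covariance method, and does not say which strata would be used.

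Section 6.1.2 lists baseline measurement of the 0-10 pain scale, the 0-10 xerostomia scale, both severity scales (Appendices B and C) and OHIP-14 ("Disease specific quality of life - OHIP-14 scale (ages 18 and older only-Appendix D"). Section 8.4.1 says the 0-10 scales will be used to "evaluate changes in oral pain and xerostomia over the course of treatment at end of study". Section 8.5 does not say whether the tested quantity is the follow-up score or its change from baseline.

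Section 4.3 stratifies randomisation by conditioning type (myeloablative or non-myeloablative). Section 8.5 does not name that factor.

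**The concern.** These scores carry the secondary hypotheses in section 8.1.2. About 36 subjects per arm are planned, and no power is stated for these comparisons. A plain two-sample Wilcoxon test takes no covariates, so the test named and the adjustment promised are not connected. A follow-up Wilcoxon, a change-score Wilcoxon, a stratified Wilcoxon and a regression model would all fit the wording, and the choice could be made after the data are seen.

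The covariate most likely to explain the follow-up score is the same score before treatment. The documents suggest that subjects will differ at entry for reasons unrelated to study drug. Section 10.3.6 notes that transplanted subjects may have reduced salivary function, which bears on xerostomia. OHIP-14 (Appendix D) asks about teeth and dentures as well as the mouth. Leaving that variation in the error term weakens the comparison, although the data to remove it are already collected.

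**Working it through.** **The plan's own figure.** Section 8.2 gives 36 per arm for 80% power, 15% versus 45%, at 0.05 (sidedness not stated). With a pooled two-sided test and no continuity correction:

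n = [1.96·√(2·0.30·0.70) + 0.8416·√(0.45·0.55 + 0.15·0.85)]² / 0.30² = (1.270 + 0.515)² / 0.09 ≈ 35.4, so 36 per arm. Power at 36 is 80.7%.

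The figure reproduces, but it concerns the primary endpoint. It is used here only for the sample size.

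**Normal-theory gain.** The correlation r between baseline and follow-up is not in the documents, so a range is assumed. Take an effect that gives 80% power without adjustment: d = (1.96 + 0.8416)·√(2/36) = 0.66 SD. Adjusting for baseline multiplies the variance by 1 − r². Analysing change multiplies it by 2(1 − r). Power is Φ(2.8016/√factor − 1.96), and the equivalent sample size with adjustment is 36/(1 − r²).

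| r | 1 − r² | Equivalent n per arm | Power, baseline-adjusted | Power, change score |
|---|---|---|---|---|
| 0 | 1.00 | 36.0 | 80.0% | 50.8% |
| 0.3 | 0.91 | 39.6 | 83.6% | 65.8% |
| 0.5 | 0.75 | 48.0 | 89.9% | 80.0% |
| 0.7 | 0.51 | 70.6 | 97.5% | 95.1% |

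**Rank-based simulation, 0-10 scale.** Settings: 36 per arm, 4,000 trials per value of r, normal latent scores (mean 2.5, SD 2.5) rounded and cut to 0-10, effect 0.66 SD. The stratified Wilcoxon test (van Elteren) splits baseline into halves.

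| r | Plain Wilcoxon | Rank ANCOVA | Stratified Wilcoxon |
|---|---|---|---|
| 0 | 72% | 72% | 71% |
| 0.3 | 74% | 77% | 76% |
| 0.5 | 72% | 82% | 78% |
| 0.7 | 74% | 92% | 87% |

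The plain test does not depend on r. Its 72-74% spread is simulation error (standard error √(0.73·0.27/4000) ≈ 0.7 points). With no treatment effect and r = 0.5, rejection rates were 5.8%, 5.6% and 5.5%.

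A separate simulation (2,500 trials per setting, effect 0.67 SD) gave about 78% for the plain test and 80%, 86% and 95% for rank ANCOVA at r = 0.3, 0.5 and 0.7. Together the gains are 2-3, 8-10 and 17-18 points.

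**Many zeros at baseline.** A third simulation (3,000 trials per setting) assumed that 50-85% of baseline pain scores are zero and that follow-up pain is raised by new oral GVHD at the plan's 45% versus 15%. The gains fell to about 0-2, 2-4 and 3-8 points at latent r = 0.3, 0.5 and 0.7. The zero fractions and the rise in pain are assumptions.

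**Severity.** Section 3 requires no evidence of oral chronic GVHD, section 4.2.1 excludes clinically significant disease, and section 8.8.2 rechecks subjects before dosing. With an assumed 85% at zero on the 6-point scale, plain Wilcoxon versus rank ANCOVA was 67% versus 67% at latent r = 0, 68% versus 68% at 0.3, 67% versus 71% at 0.5 and 68% versus 76% at 0.7.

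**Timing of the covariates.** Section 6.1.1 lists randomisation at the screening stage (days 60-90), ahead of the baseline scores in section 6.1.2. Section 3 places randomisation at days 90-100. Sections 8.2 and 8.8.2 put the baseline assessments before the first dose. The first dose is therefore the cut-off that certainly keeps the baseline scores available as covariates.

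**The case against.** A reader might infer that the plan is simply unadjusted. It is not: section 8.5 promises both covariate adjustment and stratified analyses. What is missing is the method and the two covariates.

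A reader might also infer that a Wilcoxon approach cannot deliver adjustment. That holds only for the plain two-sample test. A stratified Wilcoxon test fits the promise of stratified analyses and recovers part of the gain (78% against 72% at r = 0.5, 87% against 74% at r = 0.7). It is not specified, however, and it recovers less than rank ANCOVA.

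Nor do the documents establish that baseline is ignored. Section 8.4.1 speaks of changes in pain and xerostomia, so a change-score test is a fair reading. That would be a weak substitute at low correlation: 66% power at r = 0.3, against 80% ignoring baseline and 84% adjusting for it.

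The strongest objection concerns size. At r = 0.7 the formula gives the equivalent of 70.6 per arm, which invites the claim that adjustment nearly doubles the trial. The documents give no correlation, standard deviation or effect for any of these scores. In a prevention trial, follow-up symptoms may come largely from new disease that baseline symptoms do not predict, and the zero-heavy simulation shows how far the gain can then shrink. This objection stands and limits the claim to a range.

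It is also true that the Wilcoxon test is valid under randomisation, and that these are unpowered secondary endpoints in a pilot study.

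**Conclusion.** The point holds as a gap in specification with a likely loss of precision. Section 8.5 does not say how its promised adjustment will be made, and omits the baseline score and the conditioning stratum. For pain, xerostomia and OHIP-14 the forgone power runs from nothing at zero correlation to about 17-18 points at r = 0.7. That range rests on assumed correlations, 36 per arm and an effect of about two-thirds of an SD. It is smaller if many baseline scores are zero. For severity, expect little: 0-4 points for latent correlations up to 0.5, under the assumed floor. No figure is put on the value of including the conditioning stratum.

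The primary analysis is untouched, and nothing here makes the secondary tests invalid. This is a free improvement rather than the correction of an error.

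**What to change.** In section 8.5, make the main analysis of pain, xerostomia and OHIP-14 a rank ANCOVA or proportional-odds model of the follow-up score on treatment, the same score at baseline, and conditioning stratum. Choose one of the two models in advance, and name the visit that supplies the follow-up score, which 8.5 leaves open. Use the same model for severity for consistency, without expecting much gain. OHIP-14 remains an adults-only analysis.

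Limit the covariates in this model to values measured before the first dose of study drug. Age qualifies, as does immunosuppression recorded by then. Immunosuppressant use during the study, which section 5.2.2 tracks, does not, because treatment may influence it. Reword 8.4.1 so that change from baseline is not left as a competing analysis, and keep the Wilcoxon test as supportive.

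The cost is a few sentences of SAP text and slightly more analysis work. No new data or visits are needed. The change should be made before unblinding.
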